6.1. Data collection

Outcome measures are collected at baseline, six weeks, three, six and nine months. Data collection is performed online, and consequently all data are entered directly into the selfBACK database by the participants. The website created for data collection has been extensively tested before the start of the

trial to ensure that all items of the outcome questionnaires are included, that the structure from the original questionnaires are kept in the online version, and that the scoring for each included questionnaire is consistent with the original scoring instructions. Time to complete the baseline questionnaire is approximately 20-25 minutes, the follow-up questionnaires are shorter and time to complete is approximately 20 min.

For baseline, six weeks, three, six- and nine-month follow-up, participants will be sent an email with a link that directs them to logon to the SELFBACK questionnaire website using their username and password provided at the start of the trial. To ensure as high a response rate as possible in the follow-up questionnaires, two reminder e-mails will be sent, the first after three days and the second after six days. If still no answer, a researcher will contact the participant via text-message or by phone call and ask if he/she is willing to answer the RMDQ on the phone.

In addition to the outcomes obtained at baseline and follow-ups answered via the website, participants in the intervention group will answer a set of tailoring questions on a weekly basis in the app (described in section 3.2.1). These answers will be tracked over time as a separate dataset and used in secondary analysis of the trial data.

6.2. Access to data

Ownership of the data collected in the SELFBACK trial is shared between the participating partners (NTNU, GLA, RGU, TRX, NFA, HLE, UoSD). A data steering committee will be established, who will be competent to decide over the use of the data. The steering committee will comprise one member from each participating partner. The SELFBACK consortium supports the concept of data sharing and enquires from outside research partners to use the data are welcomed and will be discussed and decided upon by the steering committee. All personal identifiable data collected in the trial will be kept for five years. These data are kept to be able to track any adverse events reported post completion of the trial, and to enable the project to contact enrolled participants should any plan of additional long-term follow-up be funded. After this five-year period the data set will be fully anonymised. The anonymised full data set will be kept for up to 30 years for research purposes and will be used to create a data model that can inform the further development of a potential commercial version of the SELFBACK app. Data will be stored at NTNU, NO.

7. Pilot testing

A pilot study was conducted, starting August 2018 and ending January 2019. The primary reason for conducting the pilot study was to test a fully operative version of the SELFBACK app as well as to gain information about practical procedures regarding recruitment and screening as described in this protocol. Consequently, the pilot study provided information on the number of recruitment sites needed in each country and also identified challenges to the recruitment process that could be adjusted before the RCT.

The pilot was conducted with the methods described for the RCT in this protocol. Recruitment ran until recruitment had been tested from all described channels. All participants in the pilot study were given the SELFBACK app in addition to usual care (intervention). Outcomes were collected at baseline and after 6 weeks. The outcome data collected will not be included in the RCT analyses. The pilot study also informed which variable was to be selected as a measure of adherence for the RCT. The

process evaluation (see section 8) was included in the pilot. Data on app usage and participants' experiences with the app from interviews informed any adjustments needed in the app prior to the RCT.

8. Process evaluation

As an integrated part of the RCT, a process evaluation will be conducted, which explores how the digital self-management intervention will be implemented and received and used by participants. We intend to follow the RE-AIM framework [77]. The process evaluation will be informed by quantitative and qualitative data. The Virtual Climate Care Questionnaire (VCCQ) [78] (in a 15-item version) concerns perceived support for autonomy in a virtual care setting and three rating questions (on overall rating, ease of use and recommendation to others) using a 5-point system, will be collected. In addition to the questionnaires, data on physical activity (step count) and data analytics on app usage will be collected. Semi-structured interviews with a purposive sample of participants from both intervention and control groups from across DK and NO will be undertaken. These interviews will collect information from the participants about their experiences of self-management and, for the intervention group users, of using the selfBACK app to promote self-management of LBP. The interviews will also explore barriers and facilitators to engagement with the selfBACK app and embedding its use within daily routines. The qualitative components will be theoretically underpinned by the Normalization Process Theory [79, 80]. Furthermore, adoption of the intervention by clinicians and their appraisal of the self-management plans generated by the DSS will be investigated through an electronic survey to all participating clinicians and semi-structured interviews with a purposive sample of participating clinicians.

9. Trial management

9.1. Research ethics approval

Approvals for the pilot study, RCT and process evaluation have been obtained from the relevant ethical committees in DK and NO separately. In DK the approval was sought from the Regional Scientific Ethical Committee for Southern Denmark and in NO from the Regional Committee for Medical and Health Research Ethics. Correspondingly, approval from institutional review boards and/or data protection agencies have been obtained in both DK and NO. In DK, approval was obtained from the Danish Data Protection Agency through application to the University of Southern Denmark's legal office and in NO from the National Data Protection Authority.

9.2. Protocol amendments

Any amendments to the protocol will be registered with a detailed description of the change marked with date of implementation. Any amendments to the protocol will be filed with the relevant ethical committees or data protection agencies and registered at (www.clinicaltrials.gov) for transparency.

9.3. Trial monitoring

9.3.1. Harms

No serious adverse events are expected for this trial. As the suggested self-management plans may include advice to increase physical activity and exercise volume, increased muscle soreness and transient increase in joint pain are expected. Such events are known in exercise interventions and as they are transient, they pose no harm to the participants. Additionally, participants are informed that

such events may occur and that they are normal. Furthermore, any detection of unusual pain increase is automatically noted and reacted to by the DSS, and a suggestion to adjust volume of physical activity or exercise and advice on handling muscle pain is given to the participant. In addition, within the app a “caution” checklist can be consulted if participants are experiencing worsening of symptoms or pain flare-ups. In the checklist, participants are advised to seek care with their primary HCP or emergency clinics as they normally would. Consequently, as serious adverse events are unexpected, no interim analysis or a priori defined stopping rules are defined or implemented for this trial.

For each country, all enquiries from participants reporting technical or medical problems are registered. The app contains a link to a webpage with Frequently Asked Questions (FAQ) that can guide participants with technical issues. Should a participant report any worsening of symptoms, the participant will be advised to seek care from their HCP as they normally would. All enquiries will be recorded and discussed in an internal audit and reported with the study results.

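### Apart from worsening back pain, adverse events are captured only through participant-initiated enquiries, so enquiry counts are incomplete and not a reliable harms comparison between arms

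*Protocol*

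**What the plan says.** Protocol section 9.3.1 (Harms) expects no serious adverse events. It expects muscle soreness and passing joint pain from the activity and exercise advice, and has participants told that "such events may occur and that they are normal". It then describes what the app does and what the team records:

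- The collection rule, applied within each country, is that "all enquiries from participants reporting technical or medical problems are registered".
- The reporting rule is "All enquiries will be recorded and discussed in an internal audit and reported with the study results".
- For users who feel worse, "within the app a “caution” checklist can be consulted if participants are experiencing worsening of symptoms or pain flare-ups". In that checklist "participants are advised to seek care with their primary HCP or emergency clinics as they normally would".
- The decision support system also monitors symptoms: "any detection of unusual pain increase is automatically noted and reacted to by the DSS".
- On technical help: "The app contains a link to a webpage with Frequently Asked Questions (FAQ) that can guide participants with technical issues".

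Section 9.3.2 has an internal audit review the adverse events that have been reported. On the questionnaires, section 6.1 says "Outcome measures are collected at baseline, six weeks, three, six and nine months". The outcomes in sections 4.1 and 4.2 include RMDQ, average and worst pain, and Global Perceived Effect, none of them restricted by arm. There is no adverse event item among them. Section 5.2 contains no harms analysis. The SAP covers cost-effectiveness only.

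**The concern.** A register of enquiries records an event only when three things happen: the participant notices it, thinks it worth reporting, and contacts the research team rather than someone else. Each step can fail, so the register is a subset of events of unknown size.

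The steps may also work differently in the two arms. The intervention consists of advice to move and exercise more, delivered by a system that responds to symptoms itself. Controls have no such system. An arm difference in enquiries could therefore reflect contact behaviour, event rates or both, and the register alone cannot tell them apart.

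This matters because the enquiries are to be published with the results. The plan names no other safety data, so readers are likely to take them as the safety account. Protocol section 9.4 says the app may be marketed commercially. The blinded-interpretation procedure in section 5.2 is built on the primary outcome data and does not extend to harms.

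**Working it through.** The documents give no adverse event rate, harms sample size or harms analysis, so there is no stated figure to reproduce. The check is mainly textual.

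**Step 1. What is solicited in both arms, and what is not.**

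| Type of event | Scheduled question in both arms? | Source |
|---|---|---|
| Worsening of low back pain | Yes: Global Perceived Effect, pain intensity, RMDQ | Protocol 4, 4.1, 4.2 |
| Fall, injury, pain outside the back, other health problem | No dedicated question | Protocol 4.1, 4.2, 6.1 |
| Seriousness, severity, relatedness | No definition or recording rule | Protocol 9.3.1, 9.3.2 |

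The first row is a genuine safeguard, although the protocol treats these measures as efficacy outcomes. The second row depends wholly on enquiries. The audit does not close the gap, because it reviews events already reported. Participants who do not answer the questionnaire are asked by phone for the RMDQ only (section 6.1).

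**Step 2. What differs between arms.**

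| Feature | App arm | Control arm | Possible effect on enquiries from the app arm |
|---|---|---|---|
| Information on how to contact the researcher (2.5) | Yes | Same | None |
| Checklist pointing to own clinician or emergency clinic (9.3.1) | Yes | No | Lower |
| Automatic detection of, and response to, pain increase (9.3.1) | Yes | No | Lower if the user is satisfied by the response; higher if it draws attention to the event, or if the detections are counted |
| Weekly questions, including pain (4.2, 6.1) | Yes | No | Either way |

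Nothing says that automatic detections or weekly answers enter the enquiry register; section 6.1 keeps the weekly answers as a separate dataset. The message that soreness is normal may also discourage reports, but section 9.3.1 does not say whether controls receive it.

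**Step 3. What unequal capture would do (illustration; the rates and capture probabilities are assumptions).** Let n be participants per arm, p the true proportion with an event (equal in both arms), and c the probability that an event leads to an enquiry.

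- Expected count per arm = n × p × c.
- Expected ratio, app to control = c(app) / c(control). Both n and p cancel.

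With the planned n = 175 (Protocol 5.1) and p = 10%, true events per arm = 175 × 0.10 = 17.5.

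| c control | c app | Expected count, control | Expected count, app | Ratio |
|---|---|---|---|---|
| 0.50 | 0.50 | 8.8 | 8.8 | 1.0 |
| 0.50 | 0.35 | 8.8 | 6.1 | 0.70 |
| 0.50 | 0.25 | 8.8 | 4.4 | 0.50 |
| 0.35 | 0.50 | 6.1 | 8.8 | 1.43 |
| 0.25 | 0.50 | 4.4 | 8.8 | 2.0 |

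Equal incomplete capture lowers both counts but leaves the ratio at 1.0. Unequal capture distorts the ratio in either direction. In the 0.50 against 0.25 case, the chance of a nominally significant arm difference with no true difference is about 23% at p = 10% and about 60% at p = 30%. The SAP reports 461 participants included rather than the planned 350. That raises the counts but not the ratios.

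**The case against.** Several points on the other side are sound.

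- **Back-pain worsening is already solicited.** It is a central foreseeable harm, and it is asked about in both arms on the same schedule. A reader might infer that no harms comparison is possible at all. The documents do not support that; the limit applies to enquiry counts and to events other than back-pain worsening.
- **The contact route is equal.** Protocol section 2.5 gives both arms the same information on reaching the researcher. This stands. What differs is the occasion and reason to use it.
- **The direction of any bias is open.** A reader might infer that the app arm must look falsely safe. The checklist points that way, but automatic detection and weekly questions could raise awareness and reporting.
- **The FAQ page is not evidence.** It is for technical issues, so it does not plausibly divert medical reports. At most it changes the number of technical enquiries, which is a reason to tabulate them separately.
- **The plan states no between-arm test of enquiries.** It registers them by country and reports them. This stands, but once the counts are published with the results of a two-arm trial, readers will compare them, and the plan gives no warning against it.
- **A solicited item would still be self-report by unblinded participants.** It would make the question and its timing the same in both arms, but would not remove arm-dependent answering.

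The main-trial SAP, which the cost-effectiveness SAP says was published with the primary results, is not one of the two documents. It might specify how harms were reported. Nothing in the protocol indicates that further harms data were collected.

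**Conclusion.** The point holds in limited form. Apart from worsening back pain, adverse events reach the record only when a participant makes contact, with no definition and no solicited question. App-only features may make that capture unequal. Enquiry counts are therefore incomplete and should not be read as a comparison of harms by arm.

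Neither the amount of under-counting nor the direction of any arm difference can be derived from the documents. The ratios of 0.50 to 2.0 rest on assumed capture probabilities between 0.25 and 0.50 and equal true rates. They show what is possible, not what is expected. A reader might also want an upper limit on the true event rate from a low or zero count. The documents give no capture rate, so no such limit can be supported.

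This is a worthwhile, inexpensive improvement. It does not affect the primary analysis.

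**What to change.** **Collection (this design in future, or any follow-up still to come).** Add the same short closed item with free text to the six-week and three-, six- and nine-month questionnaires in both arms. It should ask about any new or worse health problem since the previous questionnaire and whether care was sought. Report the number of participants with at least one event, by arm.

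**Reporting (feasible for this trial as well).**
1. Tabulate medical enquiries by arm, separately from technical ones, and state that they were captured passively.
2. Report deterioration on Global Perceived Effect by arm as a harms measure.

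SAP section 1 says the SAP was written after the trial was completed, so only the reporting changes apply to participants whose follow-up has ended.

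**Cost.** One questionnaire item and a small amount of tabulation. The follow-up questionnaires, now about 20 minutes, become slightly longer, and the item remains unblinded self-report. It would also miss people reached only by phone, unless it is asked in that call.

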9.3.2. Auditing

On a regular basis, a researcher from each recruiting country (DK, NO), a representative from the app development company (TRX), a technical partner connected to the DSS system and primary investigator of the trial will review the recruitment, enrolment, data collection, conduct of the intervention, completion of the trial, reported adverse events and discuss appropriate actions to address any inconsistencies or unexpected events. The purpose of this internal audit is to detect any inconsistency between the planned trial conduct and the performed trial conduct as well as suggesting measures to address such inconsistencies.

9.4. Declaration of interests

The overall aim of the SELFBACK project is to develop a digital DSS and mobile app to support participants to self-manage their LBP. The results and experiences from the pilot and RCT will inform the further development of the app, which may be introduced into a commercial market. In order to secure an unbiased interpretation and dissemination of the RCT, the interpretation of the results will be performed blind to group allocation. Upon publication of study results, this commercial potential in the app development will be clearly stated and the publication will undergo peer-review to ensure methodological and scientific rigor. Additionally, the overall conduct of the trial is overseen by half-yearly review from the European Union, who is funding the project.

# Cost-effectiveness of the SELFBACK app in addition to usual care for people with low back pain: statistical analyses plan (SAP) (working title)

## Section 1: Administrative information

SAP Version 1.0 (January 2023)

This SAP is for cost-effectiveness analyses based on the SELFBACK randomised controlled trial (RCT) data. The current document supplements the SELFBACK protocol registered in ClinicalTrials.gov (NCT03798288). The paper reporting primary results from the SELFBACK trial was published in JAMA Internal Medicine with its SAP as a supplementary file, while the protocol paper was published in JMIR Research Protocols. The SAP content for the main trial was adapted from the Guidelines for the Content of Statistical Analyses Plans in Clinical Trials. The SAP for this cost-effectiveness analysis incorporates elements from the method section in the Consolidated Health Economic Evaluation Reporting Standards (CHEERS) statement and recommendations from Cost-Effectiveness Analysis Alongside Clinical Trials II—An ISPOR Good Research Practices Task Force Report. It was written after completion of the SELFBACK trial but registered in ClinicalTrials.gov before retrieving data from Danish national registry-based resources for cost-effectiveness analyses.

## Section 2: Introduction

### Background and rationale

Digital health interventions (DHIs) have immense potential as accessible, personalised tools for managing health conditions. DHIs may be important for overcoming future challenges of limited resources in the healthcare sector and are part of Denmark's digital health strategy to ensure individuals' involvement in self-management of their health conditions. Despite the potential usefulness of DHIs, there is only limited research to support the claims of cost-effectiveness. The economic value of interventions is, alongside clinical efficacy, important information for decision-makers making resource allocation decisions. Consequently, there is a need to assess the health-economic impact of their use.

One example of a DHI is the SELFBACK system. Using a self-management support system delivered through an artificial intelligence-based app, persons with low back pain (LBP) were offered individually tailored self-management concordant with national and international clinical LBP guidelines. A pragmatic RCT conducted in Denmark and Norway tested the effectiveness of the SELFBACK system as an add-on to usual care showing a small but statistically significant reduction in the primary outcomes of LBP-related disability compared to usual care at 3 months. Secondary outcomes favoured the intervention also with small effect sizes, but there were sustained results for both primary and secondary outcomes at 9 months. Danish participants in the trial consented to cross-reference their information with Danish national register data. Therefore, the data available from the SELFBACK trial makes it possible to evaluate cost-effectiveness in relation to the Danish participants.

### Objectives

The current health-economic analysis is based on a subset of participants in the SELFBACK RCT and aims to evaluate the 9 months' cost-effectiveness and cost-utility of the SELFBACK system in addition to usual care versus usual care alone.

The specific objectives are:

- (1) to assess mean per-patient additional costs associated with the SELFBACK system compared to usual care
- (2) to assess the incremental effectiveness of the SELFBACK system compared to usual care, in terms of quality of life, LBP-related disability and self-efficacy
- (3) estimate the incremental cost-effectiveness/utility of the SELFBACK system compared to usual care

## Section 3: Study Methods

### Study Design

This study is a cost-effectiveness analysis based on data from the SELFBACK trial and cost data from registers. The design, methods and results of the RCT have been reported in detail elsewhere. Still, we provide a brief overview of the RCT here.

### Settings and Participants

We recruited adults who were 18 years or older, had nonspecific LBP within the preceding 8 weeks, scored 6 points or higher on the Roland-Morris Disability Questionnaire (RMDQ) at the time of screening, had consulted a clinician (general practitioner, physiotherapist, or

chiropractor) in the region of Southern Denmark or the Trondheim municipality in Norway or had undergone a clinical examination at an outpatient spine clinic (Spine Centre of Southern Denmark) from March 8 to December 14, 2019.

A total of 461 participants were included, whereby 317 participants from Denmark and 144 from Norway. The current study is based on the data from the 300 Danish participants that provided their unique personal identification numbers, consented to the project, and further research-related use of their data beyond the RCT and are thus eligible for inclusion in this cost-effectiveness analysis. Using the personal identification numbers, data from the RCT were merged with healthcare costs and other relevant register data from Statistics Denmark and from The Danish Health Data Authority.

